### **3.2 Analyzable Time Performance Objective**

Analyzable time is the percentage of time during the wear of the Zio monitor device which yields analyzable ECG signal (i.e., free from signal artifact).

All enrolled participants in whom patch application was attempted will be included as part of the percent analyzable time analysis. However, participants who discontinue wear of the device for reasons outside of the study protocol, or occurrence of an adverse event not related to the study, will not be counted in the analysis. Full disclosure for reasons of discontinuation will be provided in the study report.

Percent analyzable time will be compared to a performance objective of 80%. The performance objective will be met if the percent analyzable time is greater than 80% in 90% of subjects.

### **3.3 Safety Measures**

All enrolled participants on whom patch application was attempted will be included in the safety analysis. The proportion of participants that experience clinically significant skin irritation through 30 days of wear will be assessed.

- Reaction severity will be assessed and reported, as follows [10]:
  - Weak Positive Reaction: Presence of erythema infiltration, discrete papules
  - Strong Positive Reaction: Presence of erythema infiltration, papules, discrete vesicles
  - Extreme Positive Reaction: Presence of bullous or ulcerative reaction, coalescing vesicles

An 'Extreme Positive Reaction' will be considered a clinically significant skin irritation.

Any skin reaction should be reported as an adverse event. Skin reactions are anticipated (see Section 12.2). All adverse events will be reviewed by a physician on the safety committee.

### 3.4 Additional Device Measures

- Signal Artifact (%) – Defined as the proportion of ECG signal that is artifact over the wear duration, reported for each study device.
- Device Functionality (%) – Defined as the proportion of Zio monitors recording a continuous ECG signal for (1) 21 days, and (2) for 30 days.

### 3.5 Other Measures

Observational assessment of participant skin types that will be reported include:

- Participant Skin Type – Dry, Oily, Normal (Baseline only)
- Known Hyperhidrosis Status – Primary, Secondary or None (Baseline only)
- Fitzpatrick Skin Type -Type I-VI (Baseline only)
- Chest Hair Density – e.g., smooth/no hair, some hair, moderately hairy, or very hairy (baseline and follow-up) in the target patch placement area

## 4.0 PARTICIPANT SELECTION AND WITHDRAWAL

### 4.1 Participant Recruitment Population and Retention

A study population representative of the intended population and who meet the study eligibility criteria will be approached for participation. iRhythm may utilize a recruitment firm such as FieldWork® or community clinics who are qualified by experience and able to support this study.

The clinics and FieldWork may utilize email solicitation, social media posting, review of their current research database of potential participants and/or flyer posting with prior approval by the IRB. Recruitment of at least 61 participants will be needed, and enrollment may continue up to a total of 75 participants for each of the two (2) phases. Seventy-five participants have already been enrolled in the first phase of this study which utilized the iRhythm legacy skin preparation process. An additional 75 participants will be enrolled utilizing an updated skin prep process. Therefore, up to 150 participants will be enrolled.

To ensure recruitment of a population representative of patients undergoing long-term continuous monitoring, age, gender, and in-clinic HCP designee vs. self-application (i.e., simulated at-home patch application) will be tracked by the study team. The following represent enrollment targets across these key groups:

- Approximately 1/3 of participants <51 years of age
- Approximately 1/3 of participants ≥51 and <70 years of age
- Approximately 1/3 of participants ≥70 years of age
- At least 40% of participants should be female
- Devices are self-applied for approximately 1/3 of the study population.

### 4.2 Participant Screening and Informed Consent

Informed consent will be obtained in-person, in the clinic. Participant screening may be performed in-person, by telephone, or by videotelephony (e.g., Zoom).

See Appendix II for assessment definitions.

#### **4.2.1 Participant Screening**

A recruitment firm (FieldWork or similar) will be utilized for initial screening. Participants who have been identified by the recruitment firm will be seen at one of two Sponsor locations (San Francisco, CA or Deerfield, IL), the Investigator or research staff, who have been trained to the Protocol, will verify all participants meet all inclusion and no exclusion criteria to determine if the potential participant is eligible for study enrollment.

Potential participants will be assigned a screening number (assigned sequentially/chronologically). An accurate and up-to-date screening log of all participants considered for the trial will be maintained at each study location. The result of the participant screening process shall be documented in the screening log to include presentation route, whether the participant met eligibility criteria (and if not, which eligibility criteria were not met), and whether the participant was subsequently enrolled.

#### **4.2.2 Informed Consent**

The Study and the Study Informed Consent Form (ICF) must receive approval by an independent IRB prior to beginning enrollment into the Study. The central IRB for this study is Advarra.

During the informed consent process, the Investigator or designee, who has been trained on the Protocol, will explain the nature and scope of the trial, potential risks and benefits of participation, and answer questions from potential participants.

All participants must sign and date the IRB-approved Informed Consent Form prior to any trial-specific procedures. Those who are not able to provide consent on their own will not be enrolled. Obtaining the consent, provision of copy to the participant, along with date and time must be documented in the participant's source documents.

The Informed Consent Form must also be signed by the investigator or designee. The Investigator or designee is responsible for advising the participant of any new information about the study or the study device(s) that may become known during the study. The consent will be administered by paper.

An authorization for use and disclosure of the participant's protected health information, in accordance with the Health Insurance Portability and Accountability Act (HIPAA), must be obtained from the participant. The requirements of HIPAA elements may be incorporated into the Informed Consent Form or it may exist as a standalone document.

#### **4.2.3 Disclosure of Participant Personal Contact Information**

In order to conduct a phone or video visit, or to follow-up regarding study-related activities with the participant, the study team at iRhythm will collect the participant's phone number and email. The participant's identity will be anonymized to the extent possible. Only those iRhythm Study Staff individuals who are directly involved with the study will have access to the participant's protected health information (PHI) for those individuals enrolled through the iRhythm clinics.

#### **4.3 Eligibility Criteria**

Participants shall be screened per the criteria listed below. Assessment for eligibility criteria will be completed through an interview with a potential participant. Participants must meet ALL of the inclusion criteria to be considered for the study. If ANY of the exclusion criteria are met, the participant is excluded from the study. Participants meeting these criteria will be approached to provide informed consent for participation in the Study and included on the screening log.

#### 4.3.1 Inclusion Criteria

Participants must meet all of the following inclusion criteria in order to participate in the study:

1. Participant must be 18 years or older at time of informed consent.
2. Participant is willing and able to provide informed consent and able to complete all visits for this study.

#### 4.3.2 Exclusion Criteria

Participants who meet any of the following exclusion criteria may not participate in the study:

1. Participant has a known allergy to adhesives.
2. Participant has a current skin infection or injury at location for study device placement.
3. Participant is a member of a vulnerable population.
4. Participant is a current or prior employee of iRhythm.
5. Participant is unable or unwilling to participate or comply with study protocol.
6. The local Investigator deems the participant has a condition that could limit their ability or willingness to participate in the study, or ability to comply with study required procedures and/or follow-up visits.
7. Participant has experienced symptomatic episodes where instance variations in cardiac performance could result in immediate danger to the participant.
8. Participant has an external cardiac defibrillator or may be exposed to high frequency surgical equipment near strong magnetic fields or devices such as MRI during the wear period.
9. Participant has a neuro-stimulator, as it may disrupt the quality of ECG data.
10. Participant does not have the competency to wear the device for the prescribed monitoring period.
11. Participant does not have the ability to consent for themselves (i.e., no LARs).

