#### 4.4 Participant Enrollment and Inclusion

Participants are considered enrolled after they have signed the Informed Consent Form and patch application has been attempted. Attempted patch application is defined as the opening of the Patch kit and initiation of the first step necessary for skin preparation.

Enrolled participants on whom patch application is attempted will be included in the analysis population. Consistent with recent FDA guidance on increasing diversity in clinical trial enrollment (Enhancing the Diversity of Clinical Trial Populations – Eligibility Criteria, Enrollment Practices, and Trial Designs: Guidance for Industry, Issued November 2020), iRhythm will attempt to implement measures to ensure that the study population reflects the characteristics of clinically relevant population. Section 4.1 above describes measures taken to ensure enrollment of a relevant population with respect to age, sex and device application (in-clinic or self-application).

In addition, diversity across races and ethnic groups will be considered in selection of study sites and through recruitment activities. The study intends to enroll a diverse group of participants representative of the US population at large.

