**VULNERABLE POPULATION (ICH E6(R3) Definition)**

Individuals whose willingness to volunteer in a clinical trial may be unduly influenced by the expectation, whether justified or not, of benefits associated with participation, or of a retaliatory response from senior members of a hierarchy in case of refusal to participate. Examples are members of a group with a hierarchical structure, such as medical, pharmacy, dental, and nursing students, subordinate hospital and laboratory personnel, employees of the pharmaceutical industry, members of the armed forces, and persons kept in detention. Other vulnerable participants include those with incurable diseases, persons in nursing homes, unemployed or impoverished persons, persons in emergency situations, ethnic minority groups, homeless persons, nomads, refugees, minors, and those incapable of giving consent.

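### Exclusion criterion 3, read through the protocol's own definition, bars ethnic minority groups whom section 4.4 sets out to recruit

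*Protocol*

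**What the plan says.** Criterion 3 reads "Participant is a member of a vulnerable population", with no qualifier, both in section 4.3.2 and in the Protocol Summary. Section 4.3 gives every exclusion full force: "If ANY of the exclusion criteria are met, the participant is excluded from the study". It also sets the method: "Assessment for eligibility criteria will be completed through an interview with a potential participant".

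The term is defined in Appendix II. The entry opens with a general test: "Individuals whose willingness to volunteer in a clinical trial may be unduly influenced by the expectation" of benefit, or of retaliation for refusing. After a first list of examples it continues: "Other vulnerable participants include those with incurable diseases, persons in nursing homes, unemployed or impoverished persons, persons in emergency situations, ethnic minority groups", followed by further groups.

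Section 4.4, directly after the exclusion list, states that "diversity across races and ethnic groups will be considered in selection of study sites and through recruitment activities" and that "The study intends to enroll a diverse group of participants representative of the US population at large".

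**The concern.** An absolute eligibility rule and a stated recruitment aim point in opposite directions for the same people. Under section 4.2.1 a recruitment firm does the initial screening, and the investigator or trained research staff then verify eligibility. The protocol gives both the same words for criterion 3 and no others. Two screeners could therefore apply it in opposite ways, and each could cite the protocol.

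On the literal reading, people whom section 4.4 seeks are turned away, and enrolling one of them is an eligibility deviation that section 8.5 requires to be reported to the sponsor. On the narrower reading neither follows. At stake are consistent eligibility decisions and the study's description of whom its sample represents.

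**Working it through.** No power or precision calculation applies; the check is of the text, plus two simple counts.

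**The chain, in version 02**

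| Step | Place | What it establishes |
|---|---|---|
| 1 | 4.3.2 and Protocol Summary, criterion 3 | Membership of a vulnerable population excludes, without exception |
| 2 | 4.3 | Meeting any one exclusion is enough |
| 3 | Appendix II | Ethnic minority groups are named among vulnerable participants |
| 4 | 4.4 | Racial and ethnic diversity is a recruitment aim |

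Steps 1 to 3 together exclude members of ethnic minority groups, which contradicts step 4.

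**Does the definition belong to criterion 3?** The criterion does not cite Appendix II. In the version 02 text available, however, the word vulnerable occurs only in the two statements of criterion 3 and in the Appendix II entry. The entry has no other use of the term to define.

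**Could criterion 3 be aimed only at minors and people unable to consent?** Both are already excluded elsewhere: minors by inclusion criterion 1, and people who cannot consent by inclusion criterion 2 and exclusion criterion 11. Criterion 3 therefore acts mainly through the other listed groups, and the protocol does not say which of them it means.

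**Does section 4.1 conflict as well?** No. It says "age, gender, and in-clinic HCP designee vs. self-application (i.e., simulated at-home patch application) will be tracked by the study team" and sets five enrolment targets: under 51 years; 51 to under 70; 70 and over; at least 40% female; about one third self-applied. Targets on race or ethnicity: 0 of 5. The conflict is with section 4.4 alone.

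**How many participants can a correction reach?**
- Planned total 150; Phase 1 enrolled 75, complete by 28 February 2025 (section 5.1), before version 02 was released on 23 April 2025 (Revision History).
- Upper bound: 150 − 75 = 75.
- Lower bound: 0, because Phase 2 enrolment to date is not stated.

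Version 01 has the same criterion, the same list and the same diversity aim, so the conflict also existed in Phase 1. How it was applied there is unknown.

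**The case against.** The strongest reply is that the literal reading is selective. The Appendix II entry begins with an undue-influence test, and the groups after it can be read as illustrations of that test rather than as separate grounds for exclusion. The surrounding text supports this. Section 4.4 speaks specifically about race and ethnicity; section 5.1 collects both at baseline to establish representation; and section 3.5 reports the full range of Fitzpatrick types I to VI. Staff who verify eligibility are trained on the protocol and so have section 4.4 before them. Nothing shows that the recruitment firm applies Appendix II at all, and no harm is demonstrated.

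Much of this stands. The sponsor probably did not intend to bar ethnic minorities, and the size given above is the reach of a correction, not a measure of harm. But these points are inference about intent. The second list names the group outright, and no passage limits criterion 3 to a case-by-case judgment. Trained verifiers work from the same words and cannot recover anyone the firm never referred. If the intended rule differs from the written one, that is a reason to correct the written one.

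**Conclusion.** The concern holds. As written, criterion 3 together with its only definition excludes people whom section 4.4 intends to enrol. This is a contradiction in the stated rule, not a detail left for another document.

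Its size is limited. Between 0 and 75 Phase 2 participants can still be reached by a change, and the 75 in Phase 1 cannot. The document gives no share of people affected, so no number excluded is claimed. The sample size, endpoints and analyses are unaffected, and no failure of the study objective follows. The conclusion assumes that the Appendix II entry defines the term used in criterion 3, which is the only use of that term found. It should be corrected, but it does not threaten the main results.

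**What to change.** Reconcile criterion 3, section 4.4 and the Appendix II entry. State in criterion 3, in both section 4.3.2 and the Protocol Summary, which of the listed groups it covers, and that ethnic minority status alone is not an exclusion. Once criterion 3 states its own scope, the Appendix II list can stay as general background. Apply the wording to any Phase 2 participants not yet screened.

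In the study report, give the number screened out under criterion 3 in each phase. The screening logs required by section 4.2.1 in both versions already record which criterion was not met. The report should add that this count does not by itself show ethnicity was the reason, and that the logs cannot show how the criterion was read for people who were enrolled or never referred.

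The cost is one IRB-approved wording change in two places and a count from existing logs. It needs no added participants, visits or procedures, and it cannot change who was enrolled in Phase 1.

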#### 4.4 Participant Enrollment and Inclusion

Participants are considered enrolled after they have signed the Informed Consent Form and patch application has been attempted. Attempted patch application is defined as the opening of the Patch kit and initiation of the first step necessary for skin preparation.

Enrolled participants on whom patch application is attempted will be included in the analysis population. Consistent with recent FDA guidance on increasing diversity in clinical trial enrollment (Enhancing the Diversity of Clinical Trial Populations – Eligibility Criteria, Enrollment Practices, and Trial Designs: Guidance for Industry, Issued November 2020), iRhythm will attempt to implement measures to ensure that the study population reflects the characteristics of clinically relevant population. Section 4.1 above describes measures taken to ensure enrollment of a relevant population with respect to age, sex and device application (in-clinic or self-application).

In addition, diversity across races and ethnic groups will be considered in selection of study sites and through recruitment activities. The study intends to enroll a diverse group of participants representative of the US population at large.

#### 4.5 Participant Payment

Participants who meet eligibility and are enrolled in the study may be eligible to receive a stipend. The recruitment firm will manage all activities for payments including reporting of the payments to the Internal Revenue Service, if required.

The amount of the participant stipend will be included in the Informed Consent Form and approved by the IRB.

#### **4.6 Participant Discontinuation**

Participants shall remain in the study until completion of the required follow-up period, unless the device experiences early detachment. The participant's involvement in any clinical study is voluntary and the participant has the right to withdraw at any time without penalty or loss of benefit. Conceivable reasons for discontinuation may include, but are not limited to, the following:

- Participant death
- Participant voluntary withdrawal
- Participant withdrawal by physician as clinically-indicated
- Participant lost-to follow-up as described below.

The Sponsor Study Staff must be notified of the reason(s) for participant discontinuation. Study staff are required to report this to the central IRB as defined by the IRB's requirements.

No additional follow-up will be required or data recorded from participants once withdrawn, except for the status (deceased/alive).

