#### **4.11 Study Participant Completion**

A participant is considered to have completed the study when any of the following has occurred:

- The participant is considered lost to follow-up per the above definition
- The participant withdraws consent
- The Investigator withdraws the participant from the Study

- The participant has died
- The Study has been completed (e.g., the participant's 30-day or final follow-up time point has been reached)
- The patch has prematurely detached from the participant (in the case of early detachment the participant should notify study staff of the date and time of detachment, and a study completion visit will be scheduled)
- The Sponsor has terminated the Study.

Sponsor must be notified of the reason for participant discontinuation. Investigators must also report this to their IRB, as required. Participants will not be replaced.

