## 5.2 Patch Wear Period

All consented participants in whom the Zio monitor Patch application is attempted will be considered enrolled in the study. Patch application is considered to have been attempted when the Zio monitor Patch kit is opened and the first step necessary for skin preparation has been initiated. The participant will be instructed to wear the device for as long as possible, up to the 30-day visit.

Study participants will be instructed to press and hold along the edges of the patch if they notice the patch peeling or lifting at the edges during the wear period. If a patch completely detaches from the participant's chest, the patch will not be re-applied. In the case of early patch detachment, the participant should notify study staff of the date and time of detachment, and a study completion visit should be scheduled as soon as possible.

At any time after patch application, if the device is determined to no longer be functioning (for example, if a rapidly blinking orange light is observed), the device will not be replaced. The date and time the determination of function failure will be noted as close to accurate as possible. As a non-functioning device does not present a safety concern, the participant will be asked to continue wearing the non-functioning patch for as long as possible, in order to record wear duration and wear experience data.

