### **5.6 30-Day (±3 days) Participant Follow-up (Visit 5)**

At day 30 following patch application and up to day 33, participants will be asked to return to the clinic and the following activities will be conducted:

- Skin assessment by HCP or designee, including photograph of the area with the device on and also upon device removal
- Adverse Event review
- Zio patch removal and visual inspection, including photograph of front and back of patch
- Patch return to iRhythm Technologies, Inc. for data download and evaluation

Participants who applied the Zio to themselves at the Baseline visit will be asked to remove the patch. They may ask a Study Staff member to provide guidance in the removal process.

Study clinical assessments and activities are summarized in **Table 2**.

Table 2: Clinical Assessment Schedule

Required Assessments to be Collected	Baseline (Visit 1)	7 & 14-Day (Visit 2 & 3)	21-Day (Visit 4)	30-Day (Visit 5)
		±3 days Phone or Video Call only	+3 days	±3 days
Informed Consent 	X	X	-	-
Medical and Cardiac Background/History	X	-	-	-
Fitzpatrick Skin Assessment	X	-	-	-
Skin Condition Assessment  , Including photograph(s)	X	-	X	X
Assessment of Device Adhesion Performance, Including photograph(s)	-	-	X	X
Adverse Events 	X 	X	X	X

1. *Continued Informed Consent will be verified at each post-baseline contact.*
2. *Including chest hair density, as applicable.*
3. *Adverse Events include serious adverse events, all device-related complications, device deficiencies, device malfunctions, procedures and any hospitalizations. If AEs are ongoing at the 30-day visit, the participant should be contacted until resolution, or Day 37, whichever is sooner.*
4. *AEs are only assessed following Informed Consent and participant enrollment into the study.*

The study device will be returned to iRhythm Technologies, Inc. for download and analysis of the ECG signal collected during the wear.

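### Contact for an unresolved skin reaction is required only from the 30-day visit, so a participant withdrawn, or completed early after detachment, has none

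*Protocol*

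**What the plan says.** All references are to protocol version 02.

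- **Withdrawal.** Section 4.6 states that "No additional follow-up will be required or data recorded from participants once withdrawn", apart from vital status. The reasons for discontinuation listed there include "Participant withdrawal by physician as clinically-indicated". There is no exception for an adverse event that is still open.
- **Early detachment.** Section 4.6 also says: "Participants shall remain in the study until completion of the required follow-up period, unless the device experiences early detachment". Section 4.11 counts it as completion when "The patch has prematurely detached from the participant". Section 5.2 adds that "a study completion visit should be scheduled as soon as possible".
- **Open adverse events.** Table 2 footnote 3 (section 5.6) reads: "If AEs are ongoing at the 30-day visit, the participant should be contacted until resolution, or Day 37, whichever is sooner". No other rule requires contact about an unresolved event.
- **Skin assessment.** Table 2 schedules it at Baseline, 21 days and 30 days and has no column for an early completion visit. The notes to Figure 1 mention only a completion form for early detachment. They list photographs at Baseline, 21 and 30 days, with optional ones at the 7- and 14-day video calls.
- **General safety text.** Section 3.3 says "Reaction severity will be assessed and reported" and has a safety committee physician review all adverse events. Section 9.1 asks source records to hold, where applicable, the participant's condition at completion or withdrawal and the resolution of reported events.

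**The concern.** Whether an unresolved skin reaction is followed depends on how the participant left the study and not on the reaction. A participant who reaches the 30-day visit with an open reaction must be contacted. One withdrawn by a physician, or completed early because the patch came off, need not be, even with the same reaction.

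Two things are at stake. The first is participant safety: nobody is required to find out how an open reaction ended. The second is completeness of the skin data. Table 3 anticipates delayed healing, which it defines by recovery after wear, so it can be observed only through contact after the patch is off. Section 3.3 includes all enrolled participants in the safety analysis, yet those who complete early have no listed final skin grading.

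**Working it through.** No figure in the plan depends on this point, so the check sets the rules side by side for each way of leaving the study with an open skin reaction.

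1. **Reaches the 30-day visit.** Skin assessment, photograph and AE review take place (5.6). Footnote 3 then requires contact until resolution or Day 37. Covered.
2. **Removes the patch because of a reaction, as section 12.2 recommends for severe ones, and stays in the study.** Section 4.6 keeps participants in until the end of follow-up unless the patch detaches early. The remaining visits and footnote 3 apply. Covered, provided staff do not class the removal as withdrawal; the protocol does not say which it is.
3. **Withdrawn by a physician, consent not withdrawn.** Section 4.6 lists this separately from voluntary withdrawal, and section 4.11 lists investigator withdrawal separately from withdrawal of consent. The 4.6 rule stops follow-up and data recording. There is no 30-day visit, so footnote 3 is never triggered. Not covered.
4. **Early detachment.** Participation ends as completion (4.6, 4.11). A completion visit is arranged (4.11, 5.2), but no skin assessment is listed for it, and footnote 3 is again not triggered. Not covered after that visit.
5. **Withdraws consent.** Stopping is legitimate.
6. **Lost to follow-up.** The participant cannot be reached, so a contact rule would not help.

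The gap is therefore routes 3 and 4.

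**Is it deliberate?** The file also contains version 01. Its footnote 3 has no contact after the 30-day visit, and its section 4.6 has the same stopping sentence. Version 02 added contact to Day 37 and left that sentence unchanged. The sponsor thus decided that open events need follow-up after wear, but tied this to one visit only.

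**Length of the existing contact.** Section 5.6 places the visit "At day 30 following patch application and up to day 33". The interval to Day 37 is 37 − 30 = 7 days for a visit on Day 30 and 37 − 33 = 4 days for a visit on Day 33. Seven days is thus the sponsor's own interval from the nominal visit day, and a reasonable limit to carry over to early exits.

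**The case against.** The strongest case on the other side is that the protocol already surrounds this gap with partial cover. Section 9.1 calls for condition at exit and for the resolution of reported events. Section 3.3 requires any skin reaction to be reported as an adverse event and reviewed by a physician. Section 6.0 has events reviewed with the investigator to decide on action, section 6.3.1 asks for event records to be updated, and section 2.5 gives participants a contact number. The Figure 1 drawing and the safety committee charter (2.5.1) are not shown, and either may say more. The note on the completion form is worded so that the form may be in addition to other content. Finally, the safety measure in section 3.3 concerns irritation during wear through 30 days, so the course after removal lies outside it.

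Much of this stands, and it makes the gap narrower. The state of the skin at exit may well be documented, and a participant can report a worsening. But none of the visible provisions requires anyone to contact a participant with an open reaction after exit. For withdrawn participants, section 4.6 says the opposite, and it sits uneasily with section 9.1's request for resolution. The possible content of Figure 1 bears on the completion visit and does not alter the 4.6 sentence or the trigger in footnote 3.

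**Conclusion.** The point holds as a minor one. Read literally, the protocol requires no follow-up of an open device- or procedure-related skin reaction when the participant is withdrawn by a physician or completes early after detachment. The readable text also lists no skin assessment at the early completion visit. The number affected is not given and is probably small. No performance objective, sample size or pass/fail result changes, and the protocol sets no safety threshold. The part about the completion visit assumes that the Figure 1 drawing adds no skin assessment.

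A reader might infer more, in four ways that the documents do not support:

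- **That everyone who takes the patch off for a reaction loses follow-up.** Someone who stays in the study keeps the remaining visits.
- **That the 25% allowance in section 7.2 measures the group.** It covers missing ECG data at the 30-day visit through device removal or loss to follow-up. The first group may stay in the study and the second cannot be reached. Neither is one of the two routes at issue.
- **That Phase 2 makes the gap worse by adding shaving and exfoliation.** The legacy instructions for use are not shown, and version 01 already refers to a shaving step, so what is new cannot be established.
- **That the loss can be stated as a number of days.** Any such figure depends on a chosen exit day, and the 7-day contact proposed below would not restore the full interval to Day 37 after an early exit.

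**What to change.** Three changes of wording:

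1. **Section 4.6.** Except ongoing device- or procedure-related adverse events from the no-follow-up rule unless the participant withdraws consent. State that removing the patch because of a reaction is not withdrawal from the study.
2. **Table 2 footnote 3.** Require contact for events ongoing at early exit or at the 30-day visit, until resolution or 7 days afterwards, whichever is sooner. For a visit on Day 33 the limit becomes 33 + 7 = Day 40, three days later than now. The heading of section 5.6 and Table 2 give a window of ±3 days, so a visit could fall on Day 27, where 27 + 7 = Day 34 would be earlier than now. Keeping Day 37 as the minimum for those who reach this visit avoids that.
3. **Early completion visit (4.11, 5.2, Table 2).** List AE review, skin grading by Table 4 and a photograph.

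The cost is an amendment with IRB approval (8.2), a grading and photograph at a visit already provided for, and a few extra contacts. Seven days will not establish whether a skin change is permanent.
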